6.4. Will any assumptions for statistical methods be checked?

Proportionality of the hazards in the Cox model will be assessed with visual inspection of Schoenfeld residuals and hypothesis testing.

For linear mixed models, normality of the measurement-level residuals will be assessed by visual inspection of histograms and q-q plots and using formal statistical testing. We will use the Shapiro-Wilk test and regard a p-value less than 0.05 as evidence of non-normality.

6.5. Will sensitivity analyses be performed?

For the primary analysis, we will conduct a sensitivity analysis by using different ratios of matching for guanabenz-treated participants and historical controls or weighted matching. For the secondary analysis, we will conduct a sensitivity analysis by using different trimmed weights Parametric models will also be used as an alternative to the Cox model.

6.6. Will subgroup analyses be performed?

A subgroup analysis will be performed on all primary and secondary efficacy outcomes based on age of onset, with participants categorized into two groups: onset <3 years of age, and onset between 3 and ≤6 years of age.

6.7. How will missing data be reported in the study reports and handled in the statistical analysis?

For incomplete diagnosis dates, a missing day will be imputed as 01. HUI inventories with more than two missing attribute scores (1%) will be excluded. Remaining missing values (up to two domains) will be imputed using pattern similarity hot deck imputation. No imputation of incomplete or missing dates for any other historical data will be done.

6.8. Will additional analyses on the primary or secondary outcomes be performed?

The same methods and reporting measures described in the primary and secondary analysis for the primary endpoint will be used to assess the effect of the treatment on overall survival.

6.9. How will harms be reported?

We will present line listings of safety outcomes. Safety outcomes will be classified by the local primary investigators as: expected complications of treatment using guanabenz; suspected unexpected serious adverse drug reactions; and other serious adverse events. Each class of safety outcome will be presented using tabulations of counts and percentages of events and of patients experiencing one or more of each type of event for each treatment arm. No formal statistical testing will be performed.

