6.1. How are the outcomes of this study defined?

The primary safety outcome is: All adverse events and serious adverse events collected from the start of study treatment until the end of the study and will be summarized for descriptive purposes.

The primary efficacy outcome is the time of loss of ambulation. Loss of ambulation is defined by the loss of walking with support.

The secondary efficacy outcomes are overall survival, HUI attributes and multiscores. Scores on the Vineland, GMFCS-MLD, ELFC-MLD, GMFM, LIPS, GMFCS, MACS CFCS and EDACS will be considered for descriptive purposes.

Other secondary outcomes are Guanabenz PK/PD parameters in plasma and will be summarized for descriptive purposes. Guanabenz exposure will also be correlated with clinical outcome measures.

For more information, please refer to pages 28 to 32 of the study protocol

6.2. Will any calculations or transformations be used to derive any outcome from the original data?

Disease duration will be calculated from age of onset until date of inclusion, screening, baseline, first day of dosing, end of titration, and visits. Ages will be calculated from the date of birth until date of inclusion, screening, baseline, first day of dosing, end of titration, and visits. Time to loss of walking, with or without support, will be calculated from the day of inclusion until the occurrence of the event.

HUI decision tables are used to generate HUI2 and HUI3 single-attribute utility scores, and applied coding algorithms to obtain overall HUI3 Health Index scores. Overall scores on the Vineland and LIPS will be calculated based on their respective domain scores.

6.3. What analysis method will be used and how will the treatment effects be presented?

For the primary efficacy outcome time to loss of ambulation, a comparison of the guanabenz-treated patients will be made with natural history data, adjusting for calendar year of symptoms onset.

For time to loss of ambulation, patients treated with Guanabenz will be matched to historical controls with a 1:2 matching ratio. The matching criteria are:

- Age of symptoms onset
- Degree of handicap regarding ambulation at comparable disease duration

Other variables might be added if considered crucial.

Primary analysis of the primary efficacy endpoint

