In the primary analysis, treated patients will be compared to their matched historical controls. We will analyze time to loss of ambulation using the Kaplan-Meier method and the log-rank test, considering the presence of clustered data. Next, the Cox proportional hazards model will be used to provide an estimate of the effect size, which will contain treatment and will be adjusted for calendar year of symptoms onset. The effects size will be reported using the Hazard Ratio (HR). We will take matching into account when estimating standard errors.

Secondary analysis of the primary efficacy endpoint

In the secondary analysis, we will use historical controls with different matching procedures and different matching ratios. We will use the Kaplan-Meier method and the log-rank test, considering the presence of clustered data. The Cox model will contain treatment and will be adjusted for calendar year of symptoms onset, reporting the effects size using the Hazard Ratio (HR).

Analysis of secondary efficacy endpoints.

The same methods that we used for the primary analysis will be used for overall survival. The HUI scores will be analyzed using linear mixed models adjusting for treatment and calendar year of age of onset. A population pharmacokinetic model will be used to assess the drug exposure (such as AUC or concentration at steady state) and this will then be used to assess the relationship with clinical outcomes using correlation or regression methods.

Descriptive analysis for primary and secondary safety endpoints

A listing of all adverse and serious adverse events will be presented for the guanabenz-treated participants, including the corresponding date and time of collection.

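### The three harm classes in SAP 6.9 leave non-serious events that are not expected complications out of every table row, although all adverse events are the primary safety outcome

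*SAP*

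**What the plan says.** SAP 6.1 defines the primary safety outcome as "All adverse events and serious adverse events collected from the start of study treatment until the end of the study" and says that it will be summarised descriptively.

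SAP 6.3, in its paragraph on descriptive safety analysis, commits to a listing: "A listing of all adverse and serious adverse events will be presented for the guanabenz-treated participants".

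SAP 6.9 starts with listings as well ("We will present line listings of safety outcomes"). It then has the local investigators sort safety outcomes into three classes: "expected complications of treatment using guanabenz; suspected unexpected serious adverse drug reactions; and other serious adverse events". Each class is to be shown "using tabulations of counts and percentages of events and of patients experiencing one or more of each type of event for each treatment arm". The section ends: "No formal statistical testing will be performed".

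SAP 4.8 defines a safety population of patients who received study medication. 6.9 does not name it as the denominator.

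**The concern.** Safety and tolerability is the primary safety objective (SAP 2.2), and 6.1 promises a summary of every AE and SAE. The tables in 6.9 are the only planned summary counts. Two of their classes are restricted to serious events by name, and the remaining one to expected complications of the drug. That leaves no class for a non-serious event that is not an expected complication.

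This group matters for tolerability. It contains newly recognised non-serious drug reactions in young children, together with the unrelated background events against which such reactions have to be judged. If 6.9 is followed as written, the report gives neither the number of these events nor the number and percentage of children who had one.

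A second weakness is that the class boundaries are not fixed. Nothing says whether a serious expected reaction belongs with the expected complications, with the residual serious events, or with both. The choice is left to whoever classifies the event.

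**Working it through.** 6.9 states no figure to reproduce, and no significance level, power or sample size enters. The check is an enumeration of event types against the three classes.

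**Event types.** Cross seriousness (yes, no) with three drug-relation categories (related and expected, related and unexpected, unrelated). This gives 2 × 3 = 6 types. Relation has to be included because the second class depends on it. Let a to f be the number of events of each type. Class 1 is expected complications, class 2 is suspected unexpected serious adverse drug reactions (SUSARs), and class 3 is the residual serious events.

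| Type | Serious? | Relation to guanabenz | Class in 6.9 |
|---|---|---|---|
| a | no | related, expected | 1 |
| b | yes | related, expected | 1, or 3, or both (see readings) |
| c | yes | related, unexpected | 2 |
| d | yes | unrelated | 3 |
| e | no | related, unexpected | none |
| f | no | unrelated | none |

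**What 6.1 requires.** All AEs = a + b + c + d + e + f. All SAEs = b + c + d.

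**What 6.9 gives.** Three readings are open, because class 1 carries no seriousness qualifier and class 3 does not say what it is other than.

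| Reading | Class 1 | Class 2 | Class 3 | Classes 2 + 3 against all SAEs | Types in no class |
|---|---|---|---|---|---|
| A: class 3 excludes classes 1 and 2 | a + b | c | d | c + d, short by b | e, f |
| B: class 3 excludes class 2 only | a + b | c | b + d | b + c + d, complete, but b is also in class 1 | e, f |
| C: class 1 is non-serious only | a | c | b + d | b + c + d, complete | e, f |

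**Results.**

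1. Types e and f have no class under any reading: 2 of 6 types. Under A and C the three classes sum to a + b + c + d, which is short of all AEs by e + f. Under B they sum to a + 2b + c + d, so the omission of e + f is partly masked by the double count of b.
2. The serious count depends on the reading. It is short by b under A and complete under B and C, with double counting between classes under B.
3. Totals of patients cannot be recovered from the class rows under any reading. One child can have events in more than one class, so numbers of patients with at least one event do not add across classes. A row for all AEs and a row for all SAEs would have to be specified, and 6.9 names neither.

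The sizes of b, e and f cannot be computed, because the SAP gives no event rates.

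**The case against.** The strongest reply is that nothing is lost. 6.3 commits to a complete listing of AEs and SAEs, 6.9 adds line listings, and with 20 to 40 treated children (SAP 3.3) a reader could count from them. 6.1 promises a summary, and nothing in 6.9 forbids extra totals. Harms are descriptive only, so no test or efficacy estimate moves. This stands as far as it goes, and it limits the severity. It does not close the gap: a listing gives no count, no number of patients with at least one event and no percentage, and the tables that are specified leave two event types out.

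A reader might infer more than the document supports, in three ways.

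- **That SAEs will be under-reported.** This follows only under reading A. It is a natural reading, but 6.9 does not state it, and under B and C every SAE is in a serious class. What can be said is that the boundary is ambiguous.
- **That the report will understate the primary safety outcome as a whole.** The complete listings rule this out. The shortfall is in the tables.
- **That a control column of harms is planned, to be left empty or read as zero.** The by-arm wording in 6.9 is a slip. SAP 7.6 calls the trial single-arm, 6.3 limits the safety listing to treated participants, and 4.8 limits the safety population to patients who received study medication.

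It is also fair that definitions of seriousness, relation and expectedness may sit in the protocol, to which 6.1 refers, or in the data validation and derivation plan cited in 7.2. Neither is at hand. They could settle where serious expected reactions go. They would not by themselves give types e and f a class, because 6.9 itself fixes the list of three.

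**Conclusion.** The point holds in a limited form. The classes in 6.9 do not cover the outcome in 6.1: non-serious unexpected reactions and non-serious unrelated events, 2 of 6 event types, fall in no tabulated class under any reading. This rests on the wording of 6.9 alone and needs no assumed rates. The table omits events as soon as one event of either type occurs. In young children followed for a year or more that is to be expected, though this is a judgement and not a figure from the SAP.

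The placement of serious expected reactions is ambiguous, and the document does not establish that SAEs are undercounted. Severity is moderate to minor. The rule concerns the only planned tabulation of a primary outcome, but every event remains in a listing and no efficacy conclusion depends on it.

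**What to change.** In SAP 6.9:

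1. Add a table of all AEs and, as a subset of it, a table of all SAEs. Show each as number of events and as number and percentage of patients with at least one, with the safety population of 4.8 as the denominator for patients.
2. Cross-tabulate each by suspected relation to guanabenz (yes, no) and expectedness (yes, no). SUSARs then become one cell of the SAE table, and serious expected reactions another. If the three existing classes are kept alongside, state whether they overlap and where serious expected reactions are counted.
3. Replace the by-arm wording with a statement that harms are reported for guanabenz-treated participants.

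The cost is a few sentences and a table shell. AEs and SAEs are already to be collected and listed. The only thing to check is that seriousness, relation and expectedness are recorded for every event, including those that fit none of the present classes.

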6.10. Which statistical software will be used to carry out the statistical analyses?

All outputs will be produced using R version 4.5.0 or a later version.

Section 7. References.

7.1. What is the title, date and version number of the current data management plan?

The current data management plan has the title "GuanabenzinVWM_Data Management Plan_V3.0_25juni2025", version number 3.0, is dated 02-07-2025 and is stored in the trial master file.

7.2. What is the title, date and version number of the current data validation and derivation plan?

The current data validation and derivation plan has the title "Data validation and derivation plan_GBZ_trial", version number 1.0, is dated 02-07-2025 and is stored in the trial master file.

7.3. Where is the study master file stored?

The trial master file is stored at the location $\underline{G:\langle divc \rangle kinderneurologie \rangle Data \ uit \ VUmc \backslash Trial}$ Master File.

7.4. Where are the syntax files for data extraction, manipulation and preparation and statistical analysis stored?

The syntax files will be stored in the trial master file.

7.5. Which standard operating procedures will be adhered to when using and analysing data from this study?

When using and analysing data from the Guanabenz clinical trial, researchers will adhere to the Amsterdam UMC standard operating procedure RDM001 Research data management.

